**NCT number (if available) : Not applicable**

**Date of the document: June 1, 2024**

This study aims to assess the effect of implementing nursing interventions on preventing medical device-related pressure injuries in critically ill patients.

Operational definition: The selected nursing interventions refer to the skin care Bundle, which includes eight key components.

Design and methods:

Research design: A parallel randomized control trial research design will be conducted.

Setting: The current study was conducted in intensive care units (ICUs) at Main Alexandria University Hospital in Egypt. Those units received patients with critical illness and immobility who were independent on nursing care to meet their basic needs.

Subjects:

This study will include a convenience sample of 120 critically ill patients who require ventilatory support. Adult patients (age  $\geq 18$  years) in the ICU who were more than 24 hours after admission were eligible for inclusion. The exclusion criteria for the patients were as follows: (i) patients who had skin diseases such as systemic lupus erythematosus and burns that may have influenced the judgment of medical device related pressure injury; (ii) patients who were not in the ICU for treatment or examination during the investigation; and (iii) patients with medical device related pressure injury before they were admitted to the ICU

Tools of the study:

Three parts make up Tool one, which evaluates general patient data.

Part one: Patients' characteristics such as age, sex, admission cause, history, length of stay, APACHE II score, body mass index, no of invasive devices used and mechanical ventilator duration.

Part two: Patient clinical assessment includes vital signs such as oxygen saturation, albumin, type of nutritional support, level of consciousness, capillary refill, and edema grade.

Part three: skin assessment. The Braden Scale for Predicting Pressure Sore Risk is defined as a pressure ulcer development risk prediction score that is based on a patient's sensory perception, skin moisture levels, activity, mobility, nutrition, friction, and shearing. Scores range from 6 to 23. A score of 15–18 indicates that the patient is at mild risk for developing a pressure ulcer; a score of 13–14 indicates moderate risk; a score of 10–12 indicates high risk; and a score of equal to or less than 9 indicates severe risk.

Two medical devices are used and consist of three parts.

Part one: ICU medical device assessment: this part is used to assess the number of non-invasive and invasive devices and whether they are needed or not. Each site will be assessed for the Pressure Ulcer Staging Form based on classification of Pressure Ulcer Grading:

Grade 1: non-blanchable erythema of intact skin. Discoloration of the skin, warmth, oedema, induration, or hardness may also be used as indicators, particularly in individuals with darker skin.

Grade 2: Partial thickness skin loss involving the epidermis, dermis, or both. The superficial ulcer presents clinically as an abrasion or blister.

Grade 3: Full-thickness skin loss involving damage to or necrosis of subcutaneous tissue that may extend down to, but not through, underlying fascia.

Grade 4: Extensive destruction, tissue necrosis, or damage to muscle, bone, or supporting structures with or without full thickness skin loss

Two medical devices are used and consist of three parts.

Method:

Ethical approval will be obtained from the university committee.

After an explanation of the study's purpose, hospitals administrative authorities' permission to perform the study was acquired from selected hospitals.

The reliability of the tool was established, and it was accepted. A pilot study was done on 10% of the studied population to assess the accessibility of two tools, and necessary modifications were made.

Data collection phase:

A letter was submitted from the Dean of the Faculty of Nursing, Damanhur University, to the director of intensive care units at the Alexandria main university in Alexandria government hospitals in Egypt.

The validity of the instruments was verified by presenting them to five experts in the field of the study, who revised them. The recommended modifications will be made.

On the first admission day, the researchers assessed all newly admitted mechanically ventilated patients to identify the exclusion criteria. They were assigned equally to controlled and intervention groups.

The patients will be assigned to two equal groups: the control (A) and intervention (B) groups.

Group A received routine nursing care for medical devices.

The intervention group (B) received skin care bundle. It includes eight key components:

Secure devices and protect the skin with dressings in high-risk areas.

K: Keep repositioning more frequently than twice daily (if not medically contraindicated); remove the medical device as soon as medically feasible.

Inspect the skin under the device more than twice daily; high-risk patients will require more frequent assessments.

Nutrition and hydration, nutrition deprivation, and insufficient dietary intake are risk factors for medical device-related pressure injuries and impaired wound healing.

Choose the correct size and type of medical device to fit the individual.

A. Avoid placing devices over sites of prior or existing pressure injury or assess the patient's risk status.

Report medical device-related pressure injuries correctly and immediately; monitor incidence and prevalence.

Educate staff on the correct use of devices and prevention of skin breakdown (younger and older patients are at high risk); never apply additional pressure when securing a device; and do not position the patient directly on a medical device unless it cannot be avoided.

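### Does the exclusion for patients not in the ICU during the investigation let assigned patients be removed from the trial?

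*Protocol*

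**What the plan says.** The protocol calls the study a randomised parallel trial: "A parallel randomized control trial research design will be conducted". It plans 120 patients in two equal groups.

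The Subjects section lists three exclusions. The first concerns skin diseases that could confuse the judgement of an injury. The second is "ii) patients who were not in the ICU for treatment or examination during the investigation". The third is "iii) patients with medical device related pressure injury before they were admitted to the ICU". The same section states the inclusion timing: patients "who were more than 24 hours after admission were eligible for inclusion".

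Under Method, the Data collection phase says when exclusions are checked: "On the first admission day, the researchers assessed all newly admitted mechanically ventilated patients to identify the exclusion criteria". The next sentence is "They were assigned equally to controlled and intervention groups".

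Among the components of the skin care bundle given to Group B is "Inspect the skin under the device more than twice daily; high-risk patients will require more frequent assessments".

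**The concern.** Of the three exclusions, only the second depends on a period whose start and end are not given. The first is a patient characteristic, and the third is tied to the time before ICU admission. *During* suggests a stretch of time, and *investigation* can mean a whole study as easily as a single assessment. Absence over a period that runs past day one cannot be known on day one. Skin inspection continues after assignment, so the mention of examination might seem to point to follow-up.

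On that reading, a patient already assigned could be excluded because of something that happened later. The groups compared would then no longer be those formed by randomisation. If leaving the ICU were related to the care received or to the risk of injury, the comparison could be biased. Two researchers could also apply the clause differently and each believe they were following the protocol. In a randomised trial this is worth checking.

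**Working it through.** The question is mainly one of reading, so the relevant statements are set side by side.

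1. **Which criteria are checked on day one.** The Data collection phase refers to the exclusion criteria as a whole. It makes no exception for the second item, so the stated check covers all three.

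2. **Order of steps.** Assignment is described directly after that check. The text gives one occasion for applying exclusions and places it ahead of assignment.

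3. **Any later check or removal.** The rest of the protocol describes the two groups' care, the assessment tools, the pilot and the permissions. None of it describes a second eligibility check or the withdrawal of an assigned patient because of absence from the unit.

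4. **What each reading needs.**
   - *Screening reading:* the patient is away from the unit when the researchers come to assess. This fits the Data collection phase with nothing added.
   - *Study-period reading:* two things must be added that the protocol does not state. The word must cover the whole study, and assigned patients who leave must then be excluded.

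5. **The inspections after assignment.** These are part of the care that Group B receives, not an eligibility procedure. Examination in the second exclusion can equally mean a clinical test that takes the patient off the unit. The bundle item therefore does not show what the exclusion means.

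6. **The available arithmetic.** Each arm has 120 / 2 = 60 patients. Let x of the 60 be injured, and let k be removed, of whom j were injured. The observed proportion changes by

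   (x − j)/(60 − k) − x/60.

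   - Largest rise, at j = 0 and x = 60 − k: 1 − (60 − k)/60 = +k/60.
   - Largest fall, at j = k and x = k: 0 − k/60 = −k/60.
   - For k = 1: 1/60 = 1.7 percentage points either way.
   - For k = 0, which is what the protocol describes: 0.

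   The extremes require that every remaining patient is injured, or that every injured patient is the one removed. The bound applies to k patients lost from any arm of 60 for any reason, so it is not evidence about this exclusion.

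7. **First admission day against more than 24 hours.** Suppose both count from the same ICU admission. The first day then covers at most hours 0 to 24, eligibility begins after hour 24, and the two windows overlap by 0 hours. They can still both hold, because the day-one step is stated to be for identifying exclusions and the 24-hour condition can be confirmed afterwards. The point concerns when eligibility is completed. It does not bear on whether assigned patients may be removed.

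**The case for a change.** The strongest case for the concern is that the Data collection phase does not say exclusions are checked *only* on the first day, and that it calls the step an assessment and not an investigation. No sentence joins the two terms. Eligibility wording belongs in a protocol, so the gap cannot simply be passed to the SAP. A clarification would cost a sentence or two and would close off exclusion after assignment for certain.

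Part of this stands. The word is undefined, *during* can denote a period, and a definition would be cheap and harmless. But the missing *only* does not create a second check. When a protocol states one time for applying its exclusions and describes assignment next, the ordinary inference is that they are applied then. Asking it also to rule out a procedure it never mentions is a preference about wording. How patients who leave the unit after assignment are handled in the analysis is commonly left to the SAP, which is not at hand, so silence on that is no finding either.

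**Conclusion.** The concern does not hold. The protocol applies its exclusion list on the first admission day, describes assignment next, and nowhere provides for excluding an assigned patient because of absence from the ICU. Carried out as written, it removes nobody after assignment under this criterion, and the effect on the comparison is zero. The harm depends on a procedure that the document does not contain.

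This rests on two assumptions: that the order of the two sentences in the Data collection phase reflects the order of the steps, and that the exclusion criteria named there are the full list under Subjects. Both are the natural reading, and nothing in the protocol contradicts them. The undefined word remains as an editorial imprecision.

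### Exclusion (iii) is tied to ICU admission rather than to assignment, and the time of assignment is unclear, so device injuries acquired in the ICU before assignment are let in

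*Protocol*

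**What the plan says.** The aim is given as "preventing medical device-related pressure injuries in critically ill patients".

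Three statements bear on who enters and when:

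- **Subjects, inclusion.** Adult patients "in the ICU who were more than 24 hours after admission were eligible for inclusion".
- **Subjects, exclusion.** The only criterion about existing device injury is "iii) patients with medical device related pressure injury before they were admitted to the ICU".
- **Method, Data collection phase.** "On the first admission day, the researchers assessed all newly admitted mechanically ventilated patients to identify the exclusion criteria". The next sentence is "They were assigned equally to controlled and intervention groups", with no day or hour attached.

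On measurement, the ICU medical device assessment under Tools of the study says "Each site will be assessed for the Pressure Ulcer Staging Form based on classification of Pressure Ulcer Grading". It names no baseline grading and does not separate new injuries from those already there. The reporting item of the skin care bundle asks staff to "monitor incidence and prevalence". That is an instruction for care, not an outcome definition.

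**The concern.** There are two linked problems.

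First, the entry times do not agree. One passage makes a patient eligible only after 24 hours. Another screens newly admitted patients on day 1 and moves straight to assignment. The passages must be reconciled.

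Second, exclusion (iii) refers to the wrong event on either timing. A prevention trial needs patients, or device sites, that are free of the injury when they are assigned. This criterion only ensures freedom from it at ICU admission. Ventilated patients carry devices from the start of their stay, and grade 1 on the staging form is erythema of intact skin, so the threshold for an injury is low.

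If an injury already present at assignment is counted as an outcome, it adds an event that the bundle could not have prevented at that site. With random assignment these events fall on both arms alike on average. The usual result is therefore dilution: a real benefit is harder to see.

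**Working it through.** **Step 1: the text under each reading**

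| Reading | Time in ICU before assignment | Does exclusion (iii) cover that time? |
|---|---|---|
| Assigned after the 24-hour criterion is met | More than 24 hours | No |
| Assigned on the first admission day | Hours | No |

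First-day screening does not close the gap. It checks the exclusion criteria, and the only one about device injury concerns the period before ICU admission.

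**Step 2: inputs for an illustration**

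- From the protocol: 120 patients in two equal groups, so 120 / 2 = 60 per arm.
- Assumed, because the protocol gives none of these: one yes/no outcome per patient; two-sided 5% test; new-injury risks of 40% against 20%, or 20% against 10%; and a share q already injured at assignment of 2%, 5%, 10% or 20%, equal in both arms.

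The protocol states no power or event rate, so there is no figure of its own to reproduce.

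**Step 3: formulas**

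Observed risk = q + (1 − q) × new-injury risk.

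Power = Φ[(d − 1.96 × SE0) / SE1], where d is the difference in observed risks, SE0 = √(2 p̄(1 − p̄)/n) with p̄ the mean of the two risks, and SE1 = √{[p1(1 − p1) + p2(1 − p2)]/n}.

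Worked line for q = 5% with 40% against 20%:

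- Control: 0.05 + 0.95 × 0.40 = 0.430. Intervention: 0.05 + 0.95 × 0.20 = 0.240.
- Risk ratio: 0.240 / 0.430 = 0.558.
- p̄ = 0.335; SE0 = √(2 × 0.335 × 0.665 / 60) = 0.0862; SE1 = √[(0.2451 + 0.1824) / 60] = 0.0844.
- Power = Φ[(0.190 − 0.1689) / 0.0844] = Φ(0.25) = 0.599.

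**Step 4: results**

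New-injury risks 40% against 20%:

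| q | Observed risks | Risk ratio | Power if counted | Power if excluded, not replaced (n per arm) |
|---|---|---|---|---|
| 0 | 40.0% vs 20.0% | 0.500 | 0.670 | 0.670 (60) |
| 2% | 41.2% vs 21.6% | 0.524 | 0.641 | 0.661 (58.8) |
| 5% | 43.0% vs 24.0% | 0.558 | 0.599 | 0.648 (57) |
| 10% | 46.0% vs 28.0% | 0.609 | 0.533 | 0.624 (54) |
| 20% | 52.0% vs 36.0% | 0.692 | 0.422 | 0.572 (48) |

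New-injury risks 20% against 10%:

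| q | Observed risks | Risk ratio | Power if counted | Power if excluded, not replaced |
|---|---|---|---|---|
| 0 | 20.0% vs 10.0% | 0.500 | 0.333 | 0.333 |
| 2% | 21.6% vs 11.8% | 0.546 | 0.300 | 0.328 |
| 5% | 24.0% vs 14.5% | 0.604 | 0.259 | 0.319 |
| 10% | 28.0% vs 19.0% | 0.679 | 0.211 | 0.305 |
| 20% | 36.0% vs 28.0% | 0.778 | 0.153 | 0.276 |

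In every row, excluding the affected patients costs less power than counting them, even without replacement.

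**The case against.** The strongest reply is that the harm depends on a counting rule the protocol never states. Dilution occurs only if an injury present at assignment is scored as an event. The aim speaks of prevention, which points to new injuries, and the handling of baseline injuries could be left to a statistical analysis plan. That is fair as to consequence. But an analysis plan can restrict counting to new injuries only if a grade was recorded at assignment, and the protocol ties no site grading to that moment. Eligibility and time of assignment are protocol content.

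A second reply is that the assignment sentence directly follows first-day screening, so assignment may well fall within hours of admission, with 24 hours meant as a minimum stay. The text does not say so, and exclusion (iii) would still refer to admission. If it is true, though, the loss is small: about 3 points of power at q = 2% (67% to 64%).

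Three further points stand:

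- The upper rows are stress tests. With new-injury risks of 20% against 10%, a q of 20% would mean as many injuries before assignment as the control arm has over all later follow-up.
- The bundle's mentions of existing injury and of prevalence are care instructions and carry little weight on how outcomes are counted.
- The bias is toward no effect only on average. With 60 per arm, chance imbalance in baseline injuries could move a single result either way.

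**Conclusion.** The concern holds and should be fixed. The two entry times conflict, exclusion (iii) is tied to ICU admission rather than to assignment, and no other passage removes or sets aside an ICU-acquired device injury present at assignment.

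The consequence is conditional: if such injuries are counted, the effect is diluted and power is lost. It is not a systematic push toward a false benefit. Its size rests on assumed risks, an assumed prevalence and a patient-level outcome. It is slight if assignment is on day 1 and could be larger if it follows the 24-hour criterion. With an outcome analysed by site, the dilution would be confined to the affected sites. Confidence is moderate: the textual gap is certain, its practical size is not.

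**What to change.** 1. State one time of assignment at which every eligibility criterion is already met. If the 24-hour criterion stays, screen from admission and assign once it is satisfied. If assignment is meant for day 1, drop that criterion; this shortens the unscreened window but keeps very short stays in the trial.
2. Under either choice, grade every device site with the existing staging form immediately before assignment.
3. Reword exclusion (iii) to cover any medical device-related pressure injury present at that check, whether it arose before or after ICU admission. If the outcome is analysed by site, exclude those sites and keep the patient.
4. Count as outcomes only injuries that first appear after assignment.

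**Cost.** A few sentences in the eligibility and data collection text, and one skin check per patient with a form already in the plan. Some screened patients become ineligible. To keep 120 assigned, the number of otherwise eligible patients needed is 120 / (1 − q): 122.4, 126.3, 133.3 or 150.0, so 123, 127, 134 or 150 at q = 2%, 5%, 10% or 20%. Patients injured early may also be those at highest risk, so excluding whole patients could narrow the population. Site-level exclusion avoids most of both losses.

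### Injury is graded per device site, with no patient-level event, observation window or common assessment schedule, so sites at risk and detection can depend on allocation

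*Protocol*

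**What the plan says.** Under Research design the protocol says: "A parallel randomized control trial research design will be conducted". Under Subjects: "This study will include a convenience sample of 120 critically ill patients who require ventilatory support". Allocation is by patient: "The patients will be assigned to two equal groups: the control (A) and intervention (B) groups".

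The one injury measurement visible is under Tools of the study, in the part on ICU medical device assessment: "Each site will be assessed for the Pressure Ulcer Staging Form based on classification of Pressure Ulcer Grading". Four grades follow. The same part counts devices: "this part is used to assess the number of non-invasive and invasive devices and whether they are needed or not".

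The group B bundle includes, under component K, "remove the medical device as soon as medically feasible". Later components call for inspecting skin beneath devices more often than twice a day and for reporting injuries at once. For the comparator there is one sentence: "Group A received routine nursing care for medical devices".

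The nearest the text comes to an outcome measure is the instruction to monitor incidence and prevalence. It sits inside the bundle's reporting component and has no unit, denominator or time point. Tool one, Part one lists length of stay and "no of invasive devices used and mechanical ventilator duration" among patient characteristics, next to age and sex.

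**The concern.** Patients are allocated and sites are graded, and nothing connects the two. The protocol does not say how several site grades become one result per patient, which grade counts as an event, or over what period.

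In many trials that would be a gap in detail. Here the intervention acts on the quantities left undefined. Removing devices changes how many sites there are and how long each is at risk. Inspecting and reporting more often changes how many injuries are found, above all Grade 1 redness, which can fade before a less frequent check. A difference between arms could then reflect the denominator, the length of observation or the intensity of looking, instead of prevention.

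An analysis plan cannot settle this afterwards. The endpoint and its schedule decide what is recorded at the bedside, and checks that were never made cannot be recovered.

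**Working it through.** **The plan's own figure.** 120 patients in two equal groups gives 120 / 2 = 60 per group. The protocol gives no event rate, effect size, significance level or power, so 120 cannot be reproduced.

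**Start and end of observation.** Subjects requires more than a day in the ICU since admission. Data collection phase describes screening on the day of admission, and assignment is the next sentence. Exclusion (iii) covers only injuries that predate ICU admission. An injury that arises in the ICU before allocation is therefore neither excluded nor separated from a new one. No end of observation is given.

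**What can differ by arm.** Early removal, frequent inspection and prompt reporting are listed for group B. Group A has routine care, not further described. No study assessment common to both arms is stated.

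All inputs below are assumptions for illustration; the document supplies none of them.

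**Denominator.** Take 5 sites per patient: 2 at 12% risk and 3 at 3%. Suppose the bundle takes away two low-risk sites and does nothing else.
- Site rate: (2×0.12 + 3×0.03)/5 = 6.6% without the bundle; (2×0.12 + 0.03)/3 = 9.0% with it.
- Patients with any injury (sites independent): 1 − 0.88²×0.97³ = 29.3% without; 1 − 0.88²×0.97 = 24.9% with.

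The site rate rises while fewer patients are injured.

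**Exposure time.** With the same hazard of 0.02 per device-day in both arms, per-site risk is 1 − exp(−0.02×10) = 18.1% over 10 days and 1 − exp(−0.02×7) = 13.1% over 7 days. The rate per 1,000 device-days is 20 in both. Different denominators give different answers from the same data.

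**Window.** At 3% per patient-day in both arms, observation for 10 v 8 days gives 1 − exp(−0.30) = 25.9% v 1 − exp(−0.24) = 21.3%.

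**Clustering, if sites were analysed as independent.** Design effect DE = 1 + (m − 1)×ICC; true type I error of a nominal two-sided 5% test = 2×[1 − Φ(1.96/√DE)].

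| Sites m | ICC | DE | True SE / naive SE | Type I error |
|---|---|---|---|---|
| 3 | 0.1 | 1.2 | 1.10 | 7.4% |
| 3 | 0.3 | 1.6 | 1.26 | 12.1% |
| 5 | 0.1 | 1.4 | 1.18 | 9.8% |
| 5 | 0.3 | 2.2 | 1.48 | 18.6% |
| 8 | 0.1 | 1.7 | 1.30 | 13.3% |
| 8 | 0.3 | 3.1 | 1.76 | 26.6% |

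With one site per patient or zero correlation, DE = 1 and nothing is lost.

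**Patient-level power at 60 v 60,** two-sided 5%, normal approximation: 50% for 30% v 15%; 67% for 40% v 20%; 79% for 30% v 10%; 82% for 50% v 25%; 88% for 40% v 15%.

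**The case against.** The strongest reply is that grading each site describes how data are recorded, not how they will be analysed. Site grades collapse readily to any injury, yes or no, for each patient. The aim speaks of patients, and exclusion (iii) treats earlier injury as an attribute of the patient. Unit of analysis and handling of clustering commonly belong to a SAP, which is not available here. This stands: a reader might infer that the trial's standard errors will be too small, but no site-level or independence-assuming analysis is stated. The type I error figures describe only what would follow from one.

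Three other inferences also go beyond the text.
- Routine care is undefined and may include early removal. The protocol shows only that removal is listed for group B.
- Nothing says that a site leaves the form once its device is gone. The protocol is silent on whether checks continue.
- Device number, ventilator duration and length of stay are listed as data to collect. No use as covariates or denominators is proposed.

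The tool description also announces three parts and shows one, so the rest might hold timing or incidence items. The finding is therefore limited to the text available. The denominator example was built to show that the direction can reverse; it is not a prediction.

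Finally, for patient-level risk over a fixed window, less device exposure is part of the bundle's effect and is not a bias. That is a reason to choose that endpoint. None of these points supplies the missing event definition, window or common schedule.

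**Conclusion.** The point holds in conditional form. In the available text the protocol fixes no patient-level event, no observation window and no outcome-assessment schedule common to both arms. Three bundle components, listed for group B only, act on sites at risk, exposure time or detection. These are protocol matters and should be corrected there.

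The harm depends on how results are reported. Per-site or prevalence results would have a denominator that treatment can change. Standard errors would be too small only if clustering by patient were ignored; the range of about 7% to 27% rests on the assumed 3 to 8 sites and correlation of 0.1 to 0.3. The size of any difference in detection cannot be estimated from the document.

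It does not follow that the trial's error bars are wrong, or that the bundle would be favoured. The examples show distortion in either direction.

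**What to change.** - Name one primary endpoint per patient: at least one new device-related injury of a stated minimum grade, at any site that has carried a device since allocation. Count every assigned patient once. The minimum grade is for the sponsor to set.
- Make a baseline skin check at allocation, so that injuries already present are not counted as new.
- Assess outcomes on one study schedule, the same in both arms and separate from the bundle's own inspections, from allocation to one fixed day. Keep checking a site after its device is removed.
- Do not treat ICU discharge or death before the fixed day as full injury-free follow-up. Simply stopping at discharge would leave the 10 v 8 day difference of 25.9% v 21.3% intact. Continue the check after discharge where feasible, or analyse time to first injury with death as a competing event. Report length of stay by arm.
- Report site-level grades as secondary, with clustering by patient.
- Treat total devices, ventilator duration and length of stay as post-allocation variables, not baseline covariates. Record devices in place and ventilator days so far at allocation as the baseline values.

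The cost is protocol wording, a few more skin checks, and fewer events than counting sites. With 60 per group, power may be modest (50% at an assumed 30% v 15%), so the sample size should be justified against the endpoint chosen.

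### Patients qualify only after 24 hours, yet existing device injury is excluded only if it preceded ICU admission, and no allocation time is fixed, so an injury that predates allocation can enter a prevention trial

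*Protocol*

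**What the plan says.** **Design.** Under Research design: "A parallel randomized control trial research design will be conducted". This is the only place where randomisation is mentioned.

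**Eligibility time.** Under Subjects, adults in the ICU "who were more than 24 hours after admission were eligible for inclusion".

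**Existing injury.** Exclusion (iii), also under Subjects, removes "patients with medical device related pressure injury before they were admitted to the ICU". No exclusion covers a device injury that arises in the ICU before allocation.

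**Screening and allocation.** Under Data collection phase: "On the first admission day, the researchers assessed all newly admitted mechanically ventilated patients to identify the exclusion criteria". The next sentence is "They were assigned equally to controlled and intervention groups", restated as "The patients will be assigned to two equal groups: the control (A) and intervention (B) groups". Neither sentence gives a sequence, a means of concealment, the person who assigns, or a time.

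**Outcome assessment.** Under Tools of the study, in the ICU medical device assessment: "Each site will be assessed for the Pressure Ulcer Staging Form based on classification of Pressure Ulcer Grading". No time of assessment and no baseline reading are attached to this form.

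**The concern.** The aim is to prevent device-related pressure injury. An injury already present at allocation cannot be prevented by anything done afterwards, so a prevention trial needs its patients free of that injury, or the injury recorded and set apart, when they are assigned. Here the rule on existing injury is tied to ICU admission, while eligibility is tied to a point more than 24 hours later. The population concerned is ventilated and carries devices throughout that interval. If such injuries enter the outcome, they add the same kind of event to both arms and hide part of any benefit.

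A second, lesser concern is allocation. The researchers who judge exclusions work immediately before an assignment step that states a ratio and nothing more. As written, it does not rule out that the next group could be foreseen. In that case, exclusion judgements could differ by group.

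**Working it through.** **Step 1. Place the three time points.**

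| Event | Time stated | Where |
|---|---|---|
| Existing device injury excluded | before ICU admission | Subjects, exclusion (iii) |
| Screening for exclusions | first admission day | Data collection phase |
| Eligible | more than 24 hours after admission | Subjects |
| Allocation | not stated; the sentence follows first-day screening | Data collection phase |

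**Step 2. Take each reading of the allocation time.**

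- *Allocation on the first admission day.* The unexcluded window between ICU admission and allocation is a matter of hours. But patients are then assigned before they meet the 24-hour criterion.
- *Allocation after the 24-hour point.* The eligibility criterion is met, but the unexcluded window is more than 24 hours. Screening on day one would not see an injury that appears later in that window, and exclusion (iii) would not remove the patient if it did.

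Screening on day one with enrolment after 24 hours is a workable sequence, so the two statements can be reconciled. The text does not do so.

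**Step 3. Effect of counting an injury that predates allocation.** Let p be the true risk of a new injury in an injury-free patient, and q the share of patients injured before allocation. If those patients count as events:

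observed risk = q + (1 - q)p

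With the same q in both arms, the q terms cancel:

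observed difference = (1 - q)(p_A - p_B)

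The difference shrinks by the factor (1 - q) and cannot change sign.

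**Step 4. Illustration with assumed inputs only.** The document gives N = 120, hence 120/2 = 60 per arm, but no event rate, effect size or q. The values below are assumptions. They show direction, and do not show that the problem occurred or how large it is. Power is by exact binomial enumeration for a two-sided 5% pooled z-test. The last column drops the injured patients without replacement, leaving 60(1 - q) = 57, 54 or 48 per arm.

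| Assumed true risks | q | Observed risks | Difference | Power if counted | Power if excluded |
|---|---|---|---|---|---|
| 40% vs 20% | 0 | 40.0% vs 20.0% | 20 points | 68% | 68% |
| | 5% | 43.0% vs 24.0% | 19 points | 61% | 66% |
| | 10% | 46.0% vs 28.0% | 18 points | 54% | 63% |
| | 20% | 52.0% vs 36.0% | 16 points | 44% | 59% |
| 30% vs 10% | 0 | 30.0% vs 10.0% | 20 points | 80% | 80% |
| | 5% | 33.5% vs 14.5% | 19 points | 70% | 79% |
| | 10% | 37.0% vs 19.0% | 18 points | 61% | 76% |
| | 20% | 44.0% vs 28.0% | 16 points | 45% | 72% |

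In every assumed case with q above zero, excluding these patients costs less power than counting their injuries.

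**Step 5. What equal groups imply about allocation.** Under simple 1:1 randomisation of 120 patients, the chance of exactly 60 and 60 is C(120, 60)/2^120 = 0.073. A planned equal split therefore suggests some restriction. Blocked randomisation and alternation would both produce it, so the wording does not tell them apart.

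**The case against.** **The document says randomised, and equal assignment does not contradict that.** This stands. A reader might infer that patients were assigned by a non-random rule. The text does not support that inference: equal groups are what restricted randomisation gives, and the description of the sample as a convenience sample concerns recruitment, not assignment. The allocation half is missing detail, not an error. It still belongs in the protocol, because how and when patients are assigned is trial conduct and not something usually left to the analysis plan.

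**The injury point is conditional.** This also stands. The assignment sentence directly follows first-day screening, so same-day allocation is a natural reading, and the window is then short. That reading, however, conflicts with the 24-hour criterion, so the timings need reconciling either way.

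**The outcome may be limited to new injuries.** The stated aim of prevention points that way, and the unseen analysis plan may say so. A reader might take the bundle item "Report medical device-related pressure injuries correctly and immediately; monitor incidence and prevalence" as proof that existing injuries are counted. It is an instruction for care in Group B, not an outcome definition, and carries no weight here. The eligibility gap remains on the text of Subjects alone.

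**Selection has limited room.** All newly admitted ventilated patients are assessed and the exclusions leave modest discretion. This is fair. A reader might also suppose that concealment makes up for the absence of any described blinding. It does not: it guards against selection before assignment, not against unblinded grading of the skin afterwards.

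**Conclusion.** The concern holds in a limited form. The eligibility time and the screening and assignment text do not yield one allocation time and must be reconciled. If allocation follows the 24-hour point, exclusion (iii) as worded admits patients whose device injury arose in the ICU before allocation.

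If those injuries are counted, the effect of the bundle is diluted by the factor (1 - q). This is conservative when q is the same in both arms, which random allocation secures on average. It would then not create a false benefit. The size of q cannot be known from the document, and the importance of the point rests on the wording of the rule, not on the assumed figures.

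The allocation step is a secondary point. It needs a stated method, and nothing in the document shows that assignment was anything other than random.

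**What to change.** 1. State one allocation time and reconcile first-day screening with the 24-hour criterion around it.
2. Record a skin check under each device at that time, before the group is known.
3. Apply the existing device-injury exclusion at allocation instead of at ICU admission.
4. Count as outcomes only injuries that arise after allocation.
5. In the allocation step, name a computer-generated 1:1 list with varying block sizes that are not disclosed, concealed from those who screen until eligibility and the baseline skin check are recorded. Fixed or known blocks would leave the list partly predictable in a trial where no blinding is described.

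The protocol mixes past and future tense, so enrolment status is unclear. If patients have already been assigned, report the method actually used and separate injuries dated before allocation, where dates exist. Relabel the design as quasi-experimental, with a correspondingly limited causal conclusion, only if assignment was not random.

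The cost is protocol wording, a list held by someone outside screening, and one added skin check per patient. A few patients may be excluded at baseline.
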